#### 4.4. Safety Analysis Set

The safety population will be used for all safety analyses and will be defined for each stage of the study.

1. The safety population for Stage 1 will include subjects who have received at least 1 dose of investigational product during Stage 1 and for whom safety data are available.
2. The safety population for Stage 2 will include subjects who received the booster vaccination and for whom safety data are available.

For the safety analysis, subjects will be analyzed according to the investigational product received.

Separate safety populations will be defined for each vaccination visit: Vaccination 1, Vaccination 2, follow-up phase for Stage 1, persistence phase, booster vaccination visit, and follow-up phase for Stage 2.

1. Vaccination 1 safety population: this population will include subjects who receive the first dose of investigational product (MenABCWY+saline or bivalent rLP2086+MenACWY-CRM) at Visit 1, and for whom safety information from Visit 1 to prior to Visit 3 is available.
2. Vaccination 2 safety population: this population will include subjects who receive the second dose of investigational product (MenABCWY or bivalent rLP2086) at Visit 3, and for whom safety information from Visit 3 up to and including Visit 4 is available.
3. Follow-up safety population for Stage 1: this population will include subjects who receive at least 1 dose of investigational product and for whom safety information is available from after Visit 4 up to and including Visit 5.
4. Persistence safety population: this population will include all subjects who signed the ICD at Visit 7. This population is analogous to the Stage 2 ITT population.
5. Booster vaccination safety population: this population will include all subjects who receive the booster dose of investigational product (MenABCWY or bivalent rLP2086) at Visit 10, and for whom safety information from Visit 10 up to and including Visit 11 is available.
6. Follow-up safety population for Stage 2: this population will include all subjects who receive the booster dose of investigational product and for whom safety information is available from after Visit 11 up to and including Visit 12.
7. Booster safety population: this population will include all subjects who receive the booster dose of investigational product at Visit 10, and for whom safety information from Visit 10 up to and including Visit 12 is available.

The safety analysis set is the primary population for the safety endpoints.

Subjects who are withdrawn early after booster vaccination during Stage 2 will be included in the follow-up safety population for Stage 2, in case they have any type of AEs in the booster vaccination follow-up interval.

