- Percentage of subjects with at least 1 AE occurring during the following time periods:
  - 30 Days after each vaccination
  - 30 Days after any vaccination
  - During the Stage 1 vaccination phase (from the first study vaccination [Visit 1] through 1 month after the second study vaccination [Visit 4])
- Percentage of subjects reporting at least 1 immediate AE after each vaccination.
- The number of days subjects missed school or work because of AEs during the Stage 1 vaccination phase (Visit 1 through Visit 4).

The following endpoints will be described after the booster vaccination in Groups 1 through 4:

- Percentage of subjects reporting local reactions (pain, redness, and swelling) and by severity within 7 days after the booster vaccination.
- Percentage of subjects reporting systemic events (fever, vomiting, diarrhea, headache, fatigue, chills, muscle pain other than muscle pain at any injection site, and joint pain) and by severity within 7 days after the booster vaccination.
- Percentage of subjects reporting the use of antipyretic medication within 7 days after the booster vaccination.
- Percentage of subjects with at least 1 SAE during the following time periods:
  - During the booster vaccination phase (from the booster vaccination [Visit 10] through 1 month after the booster vaccination [Visit 11])
  - During the booster follow-up phase (from 1 month after the booster vaccination [Visit 11] through 6 months after the booster vaccination [Visit 12])
  - From the booster vaccination (Visit 10) through 6 months after the booster vaccination (Visit 12)
- Percentage of subjects with at least 1 MAE occurring during the following time periods:
  - During the booster vaccination phase (from the booster vaccination [Visit 10] through 1 month after the booster vaccination [Visit 11])
  - During the booster follow-up phase (from 1 month after the booster vaccination [Visit 11] through 6 months after the booster vaccination [Visit 12])

- From the booster vaccination (Visit 10) through 6 months after the booster vaccination (Visit 12)
- Percentage of subjects with at least 1 NDCMC occurring during the following time periods:
  - During the booster vaccination phase (from the booster vaccination [Visit 10] through 1 month after the booster vaccination [Visit 11])
  - During the booster follow-up phase (from 1 month after the booster vaccination [Visit 11] through 6 months after the booster vaccination [Visit 12])

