**Table 6. Analysis Intervals for AEs, SAEs, MAEs, and NDCMCs**

No.	Analysis Interval	Analysis Population	Interval Start Date (Inclusive)	Interval Stop Date (Inclusive)	Safety Data
1	Within 30 days of Vaccination 1	Vax 1 safety	Vax 1 date	Vax 1 date + 30 days	AE, SAE, MAE, NDCMC
2	Within 30 days of Vaccination 2	Vax 2 safety	Vax 2 date	Vax 2 date + 30 days	AE, SAE, MAE, NDCMC
3	Within 30 days of any Stage 1 vaccination	Safety	Vax 1 date or Vax 2 date	Vax 1 date +30 days or Vax 2 date +30 days	AE, SAE, MAE, NDCMC
4	During Stage 1 vaccination phase	Safety	Visit 1 date	Visit 4 date	AE, SAE, MAE, NDCMC
5	During Stage 1 follow-up phase	Follow-up Stage 1	Visit 4 date +1	Visit 5 date	SAE, MAE, NDCMC
6	Throughout Stage 1	Safety	Visit 1 date	Visit 5 date	SAE, MAE, NDCMC
7	During booster vaccination phase	Booster vax safety	Visit 10 date	Visit 11 date (or end of booster vaccination day)	AE, SAE, MAE, NDCMC
8	During booster vaccination follow-up phase	Follow-up booster	Visit 11 date + 1, or end of booster vaccination date + 1 for early withdrawal subjects	Visit 12 date	SAE, MAE, NDCMC
9	Throughout booster phase	Booster safety	Visit 10 date	Visit 12 date	SAE, MAE, NDCMC

Abbreviations: MAE = medically attended adverse event; NDCMC = newly diagnosed chronic medical condition; vax = vaccination.

Three analysis intervals will be applied to immediate AEs (Table 7).

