### **6.1.2. Primary Safety Endpoints**

Safety endpoint data will be summarized according to vaccine received. The safety population at each corresponding AE analysis interval ([Table 6](#), [Table 7](#), and [Table 8](#)) will be used for the analysis of each AE endpoint. The primary safety endpoints will be displayed for the Stage 1 safety populations and Groups 2 and 4 combined. The primary safety endpoints for booster vaccination will be displayed for the booster safety population for Groups 1 through 4.

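### The Stage 2 follow-up safety population is worded so that early withdrawals may enter only if they have an AE, and the SAP names conflicting denominators for the primary booster safety endpoints

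*SAP*

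**What the plan says.** **Follow-up population.** Item 6 of SAP 4.4 admits boosted subjects "for whom safety information is available from after Visit 11 up to and including Visit 12". Protocol 9.7 uses the same criterion and has no clause on early withdrawal. SAP 4.4 then adds that subjects withdrawn early after the booster "will be included in the follow-up safety population for Stage 2, in case they have any type of AEs" in the booster follow-up interval. It does not say what happens to early withdrawals without an AE.

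**Interval 8.** Table 6 uses this population for the booster follow-up phase (SAE, MAE, NDCMC). The interval starts at "Visit 11 date + 1, or end of booster vaccination date + 1 for early withdrawal subjects".

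**Display population.** SAP 6.1.2 first says that the population for each interval in Tables 6 to 8 is used. It then says: "The primary safety endpoints for booster vaccination will be displayed for the booster safety population for Groups 1 through 4". SAP 4.4 defines that population as booster recipients "for whom safety information from Visit 10 up to and including Visit 12 is available". Tables 6 to 8 assign the booster rows as follows:

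| Endpoint | Population named |
|---|---|
| Table 6, interval 7 (to Visit 11) | booster vaccination safety |
| Table 6, interval 8 (follow-up) | follow-up booster |
| Table 6, interval 9 (Visits 10 to 12) | booster safety |
| Table 7, immediate AEs | booster vaccination safety |
| Table 8, 7-day reactogenicity | booster safety |

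In Table 8 the rows for Vaccinations 1 and 2 use the dose-specific populations.

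**The concern.** A denominator should be settled by exposure and follow-up, not by whether an event was reported. The added sentence mentions AE occurrence as the ground for including a withdrawn subject, and two programmers could code it differently. If it means *only if*, a withdrawn subject with an event adds one to both numerator and denominator, while an event-free subject without later contact adds to neither.

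Follow-up may itself depend on outcome. Protocol 6.5 requires AEs continuing at withdrawal to be followed, but for subjects who withdraw after the booster it asks for the next-visit procedures and the Visit 12 call only when possible.

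The affected percentages are listed among the primary safety endpoints (SAP 3.1.2), in groups of about 132 and 65. The label conflict affects the same endpoint family: for intervals 7 and 8 and for immediate AEs, SAP 6.1.2 and the tables name different populations.

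**Working it through.** **1. Stage 2 size.** 2 × 132 + 2 × 65 = 264 + 130 = 394. This agrees with Protocol 3.3 and is the planned upper limit for any booster denominator.

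**2. What the sentence touches.** Table 6 has ten booster cells (event type by interval): four in interval 7, three in interval 8, three in interval 9. Only the three in interval 8 use the follow-up population. Reactogenicity and immediate AEs do not use it.

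**3. Effect on interval 8.** The documents give no withdrawal rate, event rate or follow-up population size, so the following are assumptions:
- w, the share of booster recipients who withdraw early with no later contact: 2–15%
- p, the true risk in the interval, the same in withdrawn and other subjects: 1–10%
- f, the fraction of withdrawn subjects' events that is recorded: 0–1

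The number of booster recipients cancels.
- Reading A (*only if*): rate = [(1−w)p + wpf] / [(1−w) + wpf]
- Reading B (*as a precaution*): rate = (1−w)p + wpf

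| w | p | f | Reading A | Reading B |
|---|---|---|---|---|
| 2% | 1% | 1 | 1.02% | 1.00% |
| 5% | 5% | 1 | 5.25% | 5.00% |
| 10% | 5% | 0.5 | 5.26% | 4.75% |
| 15% | 10% | 1 | 11.56% | 10.00% |
| 15% | 10% | 0 | 10.00% | 8.50% |

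For the third row: A = (0.045 + 0.0025) / (0.90 + 0.0025) = 0.0475 / 0.9025 = 5.26%; B = 0.0475 = 4.75%.

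Over the whole range, reading A lies 0 to 1.56 points above p, and reading B lies 0 to 1.50 points below it. The ratio A/B is 1/(1−w+wpf), about 1.02 at w = 2% and up to 1.18 at w = 15%.

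In whole subjects, take 264 boosted, 26 withdrawn without contact, 12 events in the other 238, and 1 recorded event among the withdrawn. Reading A gives 13/239 = 5.44% and reading B gives 13/264 = 4.92%. The subjects with full follow-up give 12/238 = 5.04%.

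**4. Label conflict.** This does not depend on step 3. For interval 7, interval 8 and immediate AEs, SAP 6.1.2 names one population and the tables name another. For 7-day reactogenicity the two agree, but on a population defined by information up to Visit 12. If that means information must reach Visit 12, a subject with a complete 7-day diary who is lost before Visit 12 drops out of reactogenicity. If any information within the window is enough, the subject stays in. SAP 4.4 does not say which.

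**The case against.** A reader might infer that the plan builds in an upward bias in the primary booster safety rates. The documents do not support that.

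- The sentence does not say *only if*. Table 6 sets an interval 8 start for withdrawn subjects as a class, "end of booster vaccination date + 1 for early withdrawal subjects", with no AE condition. That favours the precautionary reading, under which membership does not depend on outcome and any bias runs downward. The sentence may simply be meant to cover subjects who never had a Visit 11.
- Event-free withdrawals are not necessarily excluded. Protocol 6.3.6 has the Visit 12 call attempted for all booster recipients unless consent is withdrawn, and Protocol 6.5 repeats it, when possible, for those who withdraw. Anyone reached qualifies under item 6 with or without an event.
- Only interval 8 is affected. Interval 9 reports the same three event types in a population that the sentence does not name.
- SAP 5.2.1.3 states that the safety intervals are not used to test hypotheses.
- For reactogenicity, SAP 5.3.2.1 already excludes subjects who did not receive the dose or have no data on any day, so diary availability may largely fix the denominator whatever the label.

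All of this limits direction, scope and size. It does not settle the ambiguity. The precautionary reading still conflicts with item 6 and Protocol 9.7, because it admits subjects with no later information and counts them as event-free. SAP 6.1.2 still disagrees with Tables 6 and 7 on either reading.

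**Conclusion.** The point holds as an ambiguity with a possible bias in either direction, confined to the SAE, MAE and NDCMC percentages of the booster follow-up phase, plus a separate inconsistency in the named booster denominators. A demonstrated overstatement of booster safety rates in general is not established.

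The shift is at most about +1.6 points (*only if*) or −1.5 points (*as a precaution*). Both figures rest on assumed rates and on withdrawal being unrelated to AE risk. They count only withdrawals without later contact, so the more subjects the Visit 12 call reaches, the smaller the effect. No hypothesis test and no immunogenicity conclusion is affected. The wording should still be corrected, because these are primary safety percentages and each needs one reproducible denominator.

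**What to change.** 1. Replace the early-withdrawal sentence in SAP 4.4 with a rule that does not mention AE occurrence. One option is to use all booster recipients as the denominator for intervals 8 and 9 and to report, per group, the number without Visit 12 contact. The drawback is that subjects not followed up count as event-free, which can lower the rates; the reported number shows how far this matters.
2. Use the booster vaccination safety population for interval 7, immediate AEs and 7-day reactogenicity. Interval 7 and Table 7 already do so; the booster row of Table 8 would change.
3. Reword SAP 6.1.2 so that it refers to Tables 6 to 8 and does not name a single population for all booster endpoints.
4. Reconcile SAP 4.4, SAP 6.1.2, Tables 6 to 8 and Protocol 9.7, and say whether availability up to a visit means any information in the window or information reaching that visit.

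The cost is SAP wording and a population flag. No new data are needed.

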#### 4.5. Treatment Misallocation

- Randomized into the wrong ACWY stratum: these subjects will be included in the mITT population for immunogenicity analyses if data are available and will be reported under the ACWY strata according to their true ACWY history (ACWY experience recorded on the CRF for prior ACWY history). Subjects who received prior polysaccharide meningococcal vaccine or subjects whose prior ACWY history is unknown will also be included in the mITT population as ACWY experienced. Subjects will also be included in the Stage 1 evaluable immunogenicity population as the analyses using this population are independent of ACWY history (Groups 2 and 4 combined). These subjects will also be included in the safety population for the safety analysis and will be reported under the ACWY strata according to true ACWY history.

A subject's true ACWY history will be ascertained programmatically from the prior meningococcal vaccine data set in the clinical database. Subjects having received prior monovalent C meningococcal vaccines will be determined by the sponsor's global medical monitor. Please refer to [Section 6.2.1](#) and [Section 6.2.1.2](#) as to how data from subjects having received prior monovalent C meningococcal vaccines will be reported for immunogenicity endpoints relating to MenA/C/W/Y strains.

- Vaccinated but not randomized: these subjects will be included in the safety population for safety analysis and will be reported under the vaccine group based on the vaccine received, but will be excluded from immunogenicity analyses.
- Randomized but not vaccinated: these subjects will be included in the ITT population and excluded from any safety analyses. They may be included in the mITT population if any assay results are available and will be reported under their randomized group for immunogenicity analyses.
- Randomized but received incorrect vaccine: these subjects will be included in the mITT population for immunogenicity analyses if data are available and will be reported under the vaccine group based on the randomized vaccine. These subjects will also be included in the safety population for safety analysis and will be reported under the vaccine group based on the vaccine received.

## 5. GENERAL METHODOLOGY AND CONVENTIONS

### 5.1. Hypotheses and Decision Rules

Hypothesis testing will be performed on the US evaluable subjects alone to meet the PAC objective. Similar hypothesis testing will be performed on US and ex-US subjects (combined) included in the evaluable immunogenicity Stage 1 population.

Testing will be performed on the 5 coprimary MenB endpoints, which include a 4-fold rise from baseline in hSBA titers for each of the 4 primary strains (A22, A56, B24, and B44) and the composite response (hSBA titer  $\geq$  LLOQ for all 4 primary strains combined) 1 month after the second vaccination in Stage 1.

The lower limits of the 2-sided 95% confidence intervals (CIs) must exceed each of the target lower limit for the confidence interval (LCI) values presented in Table 15 for the null hypothesis to be rejected.

The null hypothesis will be that the true proportion of subjects is less than or equal to the target LCI criterion for 1 or more coprimary endpoints. The alternative hypothesis is that the true proportion of subjects for all of the coprimary immunogenicity endpoints exceeds the target LCI.

**Table 15. Target Lower Limit of the 2-Sided 95% Confidence Interval Criteria**

	Primary Endpoint Test Strain (Variant)	Target LCI Criterion (%)
hSBA titer fold rise $\geq$ 4 from baseline	PMB80 (A22)	75
	PMB2001 (A56)	85
	PMB2948 (B24)	55
	PMB2707 (B44)	60
Composite response (hSBA titer $\geq$ LLOQ for all 4 strains combined)		65

Abbreviations: hSBA = serum bactericidal assay using human complement; LCI = lower limit of the confidence interval; LLOQ = lower limit of quantitation.

### 5.2. General Methods

Unless otherwise explicitly stated, descriptive statistics for continuous variables are n, mean, median, standard deviation (SD), minimum, and maximum. Descriptive statistics for categorical variables are: n, percentage, and total (N).

All CIs for proportions will be 2-sided 95% intervals obtained using the exact Clopper-Pearson method as described by Agresti.

## 5.2.1. Analyses for Binary Data

### 5.2.1.1. Exact Confidence Intervals

The exact CI for a proportion will be computed using the F distribution. If  $r$  equals the number of responses and  $n$  equals the number of subjects, then it follows that  $p = r/n$  is the estimate of the proportion of responses. An exact 95% CI (or Clopper-Pearson confidence limit) can be computed by solving the following 2 equations. For the lower limit  $p_L$ , use

$$p_L = \frac{rF_L}{(rF_L + (n - r + 1))} \text{ and for the upper limit } p_U, \text{ use}$$

$$p_U = \frac{(r + 1)F_U}{(n - r) + (r + 1)F_U}$$

where  $F_L$  is the quantile from the F distribution for  $\alpha=0.025$ , with numerator degrees of freedom equal to  $2r$  and denominator degrees of freedom equal to  $2(n-r+1)$ .  $F_U$  is the quantile from the F distribution for  $\alpha=0.975$ , with numerator degrees of freedom equal to  $2(r+1)$  and denominator degrees of freedom equal to  $2(n-r)$ . When  $r$  equals 0,  $F_L$  should be set equal to 1.0 so that  $p_L$  equals 0. When  $r$  equals  $n$ ,  $F_U$  should be set equal to 1.0 so  $p_U$  equals 1. The CI using the F distribution is described in Collett (1991).

### 5.2.1.2. Immunogenicity Data

Each primary MenB strain has a validated LLOQ value defined, and each secondary MenB strain and each ACWY serogroup has a qualified LLOQ (Table 16).

**Table 16. Validated hSBA LOD and LLOQs for Primary MenB Strains and Qualified LLOQs and LODs for Secondary MenB Strains and ACWY Assays**

Strain/Serogroup Type	Strain Variant/Serogroup	LOD	LLOQ
Primary MenB	A22	1:4	1:16
	A56	1:4	1:8
	B24	1:4	1:8
	B44	1:4	1:8
Secondary MenB	A29	1:4	1:8
	A06	1:4	1:16
	A12	1:4	1:16
	A07	1:4	1:8
	A15	1:4	1:8
	A19	1:4	1:16
	B16	1:4	1:8
	B09	1:4	1:8
	B03	1:4	1:8
	B15	1:4	1:8

**Table 16. Validated hSBA LOD and LLOQs for Primary MenB Strains and Qualified LLOQs and LODs for Secondary MenB Strains and ACWY Assays**

Strain/Serogroup Type	Strain Variant/Serogroup	LOD	LLOQ
ACWY	MenA	1:4	1:8
	MenC	1:4	1:8
	MenW	1:4	1:8
	MenY	1:4	1:8

Abbreviations: ACWY = *Neisseria meningitidis* group A, C, W, Y; hSBA = serum bactericidal assay using human complement; LLOQ = lower limit of quantitation; MenB = *Neisseria meningitidis* serogroup B.

All hSBA titers assessed for either MenB or MenA/C/W/Y will be analyzed as follows. At each visit where assay titers are analysed (Visits 1, 2, 3, 4, 7, 8, 9, 10, and 11), subjects with hSBA titers  $\geq$  LLOQ will be derived as follows:

- = ●, if the assay result is missing, indeterminate, or otherwise unavailable;
- = 1, if the assay result meets the specific LLOQ value;
- = 0, if the assay result does not meet the specific LLOQ value.

Similarly for all hSBA titers assessed, binary variables of assay results at each visit where assay titers are analyzed and who achieve a specific threshold ( $\geq 1:4$ ,  $\geq 1:8$ ,  $\geq 1:16$ ,  $\geq 1:32$ ,  $\geq 1:64$ , and  $\geq 1:128$ ) will also be derived.

- = ●, if the assay result is missing, indeterminate, or otherwise unavailable;
- = 1, if the assay result meets the specific threshold value;
- = 0, if the assay result does not meet the specific threshold value.

A composite response will be computed for Stage 1, 1 month after the second vaccination (Visit 4). The composite response is defined as subjects who have assay results that are  $\geq$  LLOQ for all 4 of the primary MenB strains at the same visit.

- = ●, if the assay result is missing, indeterminate, or otherwise unavailable for at least 1 of the 4 MenB primary strains;
- = 1, if all 4 MenB primary strains have assay results  $\geq$  LLOQ at the same visit;
- = 0, if not all 4 MenB primary strains have assay results  $\geq$  LLOQ.

In [Section 6.4](#), a supportive analysis is included describing different handling of missing values for the composite response.

For MenB-related endpoints, the 4-fold response in assay titers from baseline (Visit 1 prevaccination) to 1 month after the second vaccination (Visit 4) will be defined as follows:

- For subjects with a baseline hSBA titer < LOD or an hSBA titer of <1:4, a 4-fold response is defined as an hSBA titer of  $\geq 1:16$  or the LLOQ (whichever titer is higher).
- For subjects with a baseline hSBA titer of  $\geq$  LOD (ie, hSBA titer of  $\geq 1:4$ ) and < LLOQ, a 4-fold response is defined as an hSBA titer of  $\geq 4$  times the LLOQ.
- For subjects with a baseline hSBA of > LLOQ, a 4-fold response is defined as an hSBA titer of  $\geq 4$  times the baseline titer.

The 4-fold response variable for the 4 MenB primary strains will be computed as:

= •, if the assay result at baseline or specific time point is missing, indeterminate, or otherwise unavailable;

= 1, if the assay result meets 1 of the 3 definitions for a 4-fold response;

= 0, if the assay result does not meet 1 of the 3 definitions for a 4-fold response.

